9.2. Sample Size Determination

For Cohorts 1 - 3, approximately 24 participants will be randomized to receive one of three dose levels of LY3819253 or placebo. Additional participants may be required to ensure a minimum of 8 participants in each cohort complete 7 days of study assessments. Up to a maximum of 3 additional participants per cohort may be added.

Participant viral loads over time were simulated using a representative PK/PD model to enable a Monte Carlo assessment of the power of the trial to detect a 30% treatment difference in mean AUC (28 day) of viral load. This assessment revealed greater than 90% probability of meeting the following Bayesian critical success factor:

Pr ((mean AUC_{PL} – mean AUC_{LY})/ mean AUC_{PL} > 0.3) > 0.60 PL = placebo, LY = LY3819253

Additionally, the anticipated 6 participants per treatment provides greater than 80% probability (within each treatment arm) of observing safety events of reasonable prevalence (that is, at least 25%) to support the primary objective of safety assessment.

For the optional Cohort 4, up to 100 participants may be randomized in an approximate 1:1 ratio to receive either LY3819253 or placebo. The overall numbers of participants randomized to LY3819253 and placebo in this study will provide 60% power to detect a reduction in the rate of clinical worsening from 22% to 9% (one-sided alpha=0.05). Clinical worsening is defined as the proportion (percentage) of participants with any worsening on the NIAID ordinal scale from baseline to Day 15.

A participant is only allowed to receive one IV infusion in one cohort.

9.3. **Populations for Analyses**

This table defines the populations for analysis.

Population	Description
Entered	All participants who sign the informed consent form
Safety	All participants randomly assigned and who received study intervention.
	Participants will be analyzed according to the intervention they actually
	received.
Pharmacokinetic	All randomized participants who received study intervention and have
	evaluable PK sample. Participants will be analyzed according to the
	intervention they actually received.
Pharmacodynamic	All randomized participants who received study intervention and provided at
	least one post-baseline measure for the relevant endpoint. Participants will be
	analyzed according to the intervention they actually received.

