• Only quantifiable concentrations will be used to calculate PK parameters with the exception of special handling of certain concentrations reported below the lower limit of quantification (BQL). Serum concentrations reported as BQL will be set to a value of zero when all of the following conditions are met:

- The compound is non-endogenous.
- The samples are from the initial dose period for a patient or from a subsequent dose period following a suitable wash-out period.
- The time points occur before the first quantifiable concentration.
- All other BQL concentrations that do not meet the above criteria will be set to missing.
- Also, where two or more consecutive concentrations are BQL towards the end of a profile, the profile will be deemed to have terminated and therefore any further quantifiable concentrations will be set to missing for the calculation of the PK parameters unless it is considered to be a true characteristic of the profile of the drug.

Individual Concentration vs. Time Profiles

- Individual concentrations will be plotted utilizing actual sampling times.
- The terminal point selections will be indicated on a semi-logarithmic plot.

Average Concentration vs. Time Profiles

- The average concentration profiles will be graphed using scheduled (nominal) sampling times.
- The average concentration profiles will be graphed using arithmetic average concentrations.
- The pre-dose average concentration for single-dose data from non-endogenous compounds will be set to zero. Otherwise, only quantifiable concentrations will be used to calculate average concentrations.
- Concentrations at a sampling time exceeding the sampling time window specified in the protocol, or $\pm 10\%$, will be excluded from the average concentration profiles.
- Concentrations excluded from the mean calculation will be documented in the final study report.
- A concentration average will be plotted for a given sampling time only if 2/3 of the individual data at the time point have quantifiable measurements that are within the sampling time window specified in the protocol or ± 10%. An average concentration estimated with less than 2/3 but more than 3 data points may be displayed on the mean concentration plot if determined to be appropriate and will be documented within the final study report.

Treatment of Outliers during Pharmacokinetic Analysis

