10.4 Pharmacodynamic Assessment

10.4.1 Pharmacodynamic Analysis

The PD endpoints for this study are:

- Change from baseline in SARS-CoV-2 viral load (Days 7, 11, 15 and 22)
- Viral load AUC (Day 1 to 29)
- Proportion of participants that achieve SARS-CoV-2 clearance (Days 7, 11, 15, 22)
- Time to SARS-CoV-2 clearance
- Viral resistance to LY3819253 (from baseline to Day 29)

Viral clearance is defined as two consecutive negative SARS-CoV-2 values from the nasopharyngeal swabs. When deriving clearance, any missing data from the nasopharyngeal swabs will be set to positive. Time to SARS-CoV-2 clearance is defined as the earliest timepoint of the two.

If these two negative values are followed by a subsequent positive value, this measurement will be flagged and considered for evaluation of viral mutation or resistance.

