10.4.2 Pharmacodynamic Statistical Methodology

SARS-CoV-2 viral load

SARS-CoV-2 viral load will be measured using the cycle time (CT) from a polymerase chain reaction (PCR) assay. Higher CT values indicate a lower viral load.

SARS-CoV-2 viral load, including changes from baseline, will be summarized and plotted by treatment, and listed. Baseline is defined as the Day 1 predose assessment. Overlaying individual profiles of SARS-CoV-2 viral load data will also be presented graphically over time.

Changes from baseline in SARS-CoV-2 viral load data will be statistically analyzed using a mixed model for repeated measures (MMRM). The model will contain baseline as a covariate, treatment, day and treatment-by-day interaction as fixed effects, and subject as a random effect. The unstructured covariance matrix will be selected initially; if this analysis fails to converge another covariance structure will be selected based on AIC and BIC values. The least square (LS) means and treatment differences (LY3819253 minus pooled placebo at each dose level) will be calculated and presented with their corresponding 90% confidence intervals (CIs). All available data will be used in the analysis.

An example of the SAS code that will be used is as follows:

```
proc mixed data=xxx;
class trtmnt subject day;
model chg = base trtmnt day trtmnt*day / alpha=0.1 cl ddfm=kr2;
repeated day / subject=subject type=un;
lsmeans trtmnt*day / alpha=0.1 cl pdiff;
ods output lsmeans=lsm01 diffs=diff01;
run;
```

where chg is the change from baseline, base is the baseline in SARS-CoV-2 viral load data, day is the study day, and trtmnt is the treatment used in the comparison.

A Bayesian linear mixed effect model will be fitted to evaluate the critical success factor by Lilly statistics group with the model listed below:

 $y_{ijk} = \mu + \alpha \times base + \alpha_i + \beta_k + (\alpha\beta)_{ik} + \varepsilon_{ij} + \varepsilon_{ijk}$

Where y_{iik} : the change from baseline for treatment i, subject j at day k

μ: a constant common to all observations

 α : a fixed coefficient on the covariate baseline viral load

 $\alpha_{i:}$ a parameter corresponding to treatment i

 $\beta_{k:}$ a parameter corresponding to day k

 $(\alpha\beta)_{ik:}$ an interaction parameter corresponding to treatment i and day k

 ϵ_{ij} , ϵ_{ijk} : random error for between and within subject variability

prior μ , α , α_{i} , β_{k} , $(\alpha\beta)_{ik} \sim N(0, 100)$

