 $\varepsilon_{ij} \sim N(0, \sigma_1), \ \varepsilon_{ijk} \sim N(0, \sigma_2)$

 $\sigma_{1}, \sigma_{2} \sim uniform(0, 100) \text{ or } igamma(0.01, 0.01)$

the posterior of the following quantity will be assessed:

 $pr(\Delta_{anyLYdose} - \Delta_{placebo} < -0.3) > 0.6 \text{ at Day 7, 11, 15, and 22 in log base 10 scale.}$

SARS-CoV-2 viral load AUC

The AUC from Day 1 predose to Day 29 (AUC[0-D29]) will be calculated according to the linear trapezoidal rule using the measured SARS-CoV-2 viral load-time values above the lower limit of quantification. No imputations of missing data will be conducted. No AUC(0-D29) values will be calculated when Day 1 predose and/or Day 29 values are missing, or if there are more than 3 values missing in the profile.

The AUC(0-D29) will be summarized and plotted by treatment and listed.

Additionally, AUC(0-D29) data will be statistically analyzed using a linear model. The model will contain treatment as a fixed effect and baseline viral load as a covariate. The least square (LS) means and treatment differences (LY3819253 minus pooled placebo at each dose level) will be calculated and presented with their corresponding 90% confidence intervals (CIs). All available data will be used in the analysis.

An example of the SAS code that will be used is as follows:

```
proc mixed data=xxx;
class trtmnt;
model AUC = base trtmnt / alpha=0.1 cl ddfm=kr2;
lsmeans trtmnt / alpha=0.1 cl pdiff;
ods output lsmeans=lsm01;
ods output diffs=diff01;
run;
```

where AUC is the AUC(0-D29) data, trtmnt is the treatment used in the comparison, and base is the baseline viral load.

Similar Bayesian model listed in Section 10.4.2 by removing the day, interaction, and within subject error term will be applied for AUC measure analysis.

SARS-CoV-2 clearance

The proportion of patients that achieve SARS-CoV-2 clearance will be summarized by treatment in frequency tables, and listed.

In addition, the number of patients that achieve SARS-Cov-2 clearance will be analyzed using a Chi-square test to compare LY3819253 versus pooled placebo at each dose level, if there are sufficient data available.

An example of the SAS code that will be used is as follows:

```
proc freq data=xxx;
weight count;
table trtmnt*clear / chisq all;
run;
```

where trtmnt is the treatment used in the comparison, clear is the SAR-CoV-2 clearance (yes/no), and count is the corresponding number of patients.

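### The SAP does not say how a collected negative or below-LLOQ swab enters the viral-load AUC to Day 29, or on what scale that AUC is computed

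*SAP*

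**What the plan says.** **AUC rule (SAP 10.4.2, viral load AUC).** The area is a linear trapezoid "using the measured SARS-CoV-2 viral load-time values above the lower limit of quantification. No imputations of missing data will be conducted". The next sentence adds: "No AUC(0-D29) values will be calculated when Day 1 predose and/or Day 29 values are missing". The same applies when over three values are missing. The AUC is then modelled on treatment and baseline viral load: "The least square (LS) means and treatment differences (LY3819253 minus pooled placebo at each dose level) will be calculated". A reduced form of the Bayesian change-from-baseline model is also applied to it.

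**Neighbouring rules.** For serum drug concentrations, SAP 10.3.1 has a rule: "Serum concentrations reported as BQL will be set to a value of zero when all of the following conditions are met"; BQL values that do not meet those conditions become missing. For viral clearance, which requires two negative swabs in a row, SAP 10.4.1 says: "When deriving clearance, any missing data from the nasopharyngeal swabs will be set to positive". Neither rule is extended to the viral-load AUC.

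**Scale.** SAP 10.4.2 states: "SARS-CoV-2 viral load will be measured using the cycle time (CT) from a polymerase chain reaction (PCR) assay", and adds: "Higher CT values indicate a lower viral load". A log base 10 scale is named only for the Bayesian criterion on change from baseline at Days 7, 11, 15 and 22. The AUC text, its SAS code and the Bayesian AUC model name none.

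**Role.** The AUC is a secondary endpoint. Protocol 9.2 and SAP 8 size Cohorts 1-3 on it, through a "Monte Carlo assessment of the power of the trial to detect a 30% treatment difference in mean AUC (28 day) of viral load".

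**The concern.** Negative swabs are expected results in this trial, since clearance is defined by them. The AUC rule excludes them from the area without saying what their exclusion means. Two readings are open.

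- **Reading 1: a below-LLOQ swab counts as missing.** Anyone below the LLOQ on Day 29 then has no AUC, however complete the swabs. Entry to the analysis depends on the outcome that treatment is meant to change, and those who remain are the slow clearers.
- **Reading 2: the point is only skipped.** The area then stops at the last quantifiable swab, on different days in different participants. This fits a Day 1 to Day 29 area poorly, but the text does not exclude it.

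The unstated scale determines how much this matters. At stake are how many of 6 participants per dose contribute, and whether the estimated reduction means what it appears to mean.

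**Working it through.** **The plan's own figure.** The probability of more than 90% in Protocol 9.2 and SAP 8 cannot be reproduced. The PK/PD model, variance, LLOQ and AUC scale behind it are not given, so nothing below tests it.

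**Inputs from the documents.** Swabs on Days 1, 3, 7, 11, 15, 22 and 29 (Protocol 1.3); 6 participants per dose; 2 placebo in each of Cohorts 1-3, so 3 × 2 = 6 pooled. The documents give no viral loads, LLOQ or decline rates; those used here are assumed.

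**1. Evaluability under reading 1.** Let p be the share below the LLOQ on Day 29. For n = 6, P(at most one AUC) = p^6 + 6(1 − p)p^5.

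- p = 0.5: 0.0156 + 0.0938 = 0.109
- p = 0.7: 0.1176 + 0.3025 = 0.420
- p = 0.9: 0.5314 + 0.3543 = 0.886

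With p = 0.5 in pooled placebo, the chance that both groups have at least two AUCs is 0.891 × 0.891 = 0.793, 0.891 × 0.580 = 0.516 or 0.891 × 0.114 = 0.102 for those three values of p in the dose group.

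**2. Worked example (assumed LLOQ 3 log10).** Two participants share 6, 5.5, 5, 4.5, 4 through Day 15. The first then has 3.1 on Days 22 and 29, the second 2.9. The area to Day 15 is 11.5 + 21 + 19 + 17 = 68.5. The first participant adds 7(4 + 3.1)/2 + 7(3.1) = 24.85 + 21.70, total 115.05.

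| Second participant's below-LLOQ swabs | AUC (log10-days) | Gap from first |
|---|---|---|
| log10(LLOQ/2) = 2.699 | 110.84 | 4.2 |
| LLOQ = 3 | 114.00 | 1.05 |
| 0 log10 | 82.50 | 32.55 |
| Skipped (reading 2) | 68.50 | 46.55 |
| Missing (reading 1) | none | – |

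A tenfold unit change shifts every log10 value by 1. The first AUC moves by 28 and the skipped AUC by 14, so the reading 2 gap becomes 46.55 ± 14 = 60.55 or 32.55. With log10(LLOQ/2) both AUCs move by 28 and the gap stays at 4.2.

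On a linear copies scale the first AUC is 2,543,393. The second is 2,535,424 with LLOQ/2 and 2,495,174 if skipped, which is 0.3% and 1.9% below the first. Early high values dominate, so skipping matters little.

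**3. Simulation (assumed inputs).** There were 12 scenarios: baseline mean 5 or 6 log10 (SD 1.5); LLOQ 2 or 3 log10; placebo decline 0.12, 0.16 or 0.20 log10/day; LY3819253 decline 50% faster; residual SD 0.6; quantifiable baseline required. Slopes were normal (cut at 0) or lognormal. The effect is the treatment coefficient from the SAP model, placebo minus LY3819253, in log10-days. Ranges cover the scenarios.

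| Handling, slope CV 30% | Effect |
|---|---|
| log10(LLOQ/2) | 7 to 17 |
| LLOQ | 6 to 16 |
| 0 log10 | 17 to 26 |
| Reading 1, normal slopes | −1 to 8 |
| Reading 1, lognormal slopes | 4 to 10 |
| Reading 2 | 18 to 28 |
| Reading 2, tenfold unit change | 21 to 34 |

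Under reading 1 at this CV, 6-64% of placebo and 1-33% of LY3819253 participants are evaluable.

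- **CV 50%:** reading 1 gives −3 to 2 (normal) or 3 to 7 (lognormal), against 7 to 16 with log10(LLOQ/2).
- **CV 0%:** reading 1 gives 9 to 17 against 7 to 18, so there is little attenuation; it was not estimable in 3 of 12 scenarios.
- **No treatment effect, varying slopes:** evaluability is equal between arms, and every reading lies within about 0.7 log10-days of zero.

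**The case against.** **Reading 1 may not be intended.** SAP 10.4.1 treats negative swabs and missing swabs as different things, and SAP 10.4.2 puts the LLOQ and the missing-value rules in separate sentences. This weighs against reading 1, and the evaluability and attenuation figures depend on it. It does not settle the matter: the serum rule in SAP 10.3.1 turns most BQL values into missing ones, and setting reading 1 aside leaves reading 2, with its own problem on a log10 scale.

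**The magnitudes are assumed.** This stands. Lower evaluability on LY3819253 follows from the assumed faster decline, and the worked example sits just either side of an assumed LLOQ.

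**A reader might infer that the AUC will be taken on CT, so that the sizing criterion has the wrong sign.** The documents make that unlikely. The criterion was evaluated on simulated viral loads, the Day 7-22 success rule seeks a LY3819253-minus-placebo difference below −0.3 in log10, and a lower limit of quantification suits viral quantity better than CT. The practical gap is log10 against linear, plus an unstated conversion.

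**Impact is limited.** Protocol 9.1 makes all comparisons exploratory and the primary objective is safety. The Day 7-22 MMRM needs no Day 29 value. The clearance analyses are not equally free of it: a first negative on Day 22 needs a negative Day 29 swab to count.

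**A rule may exist elsewhere.** The TFL shells and the text of SAP 14.3 (listed in its contents as covering insufficient data) were not available, so this cannot be excluded.

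**Conclusion.** The concern holds and should be fixed. As written, the SAP allows more than one AUC from the same swabs. On a log10 scale neither open reading is satisfactory: participants below the LLOQ on Day 29 are dropped, or their area is cut short by an amount that depends on the unit.

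The harm shown is lost precision and a distorted effect size. Reading 1 can leave few of 6 per dose and attenuate a real effect when decline rates vary. Reading 2 gives 18 to 28 log10-days where log10(LLOQ/2) gives 7 to 17. On a linear scale, skipping hardly matters. These sizes rest on assumed viral loads, LLOQ and decline rates.

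Two stronger conclusions are not supported. The AUC analysis is not shown to produce a false signal: with no effect, the simulated difference stays near zero. Nor is the sizing probability shown to be wrong, because its inputs are not given.

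**What to change.** In SAP 10.4.2:

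1. Treat every collected negative or below-LLOQ swab as an observed value through Day 29, at one prespecified value on the stated scale (for example LLOQ/2, or its log10).
2. Apply the Day 1, Day 29 and more-than-three-missing exclusions only to swabs not taken or failed.
3. State whether the AUC is on log10 or linear viral load, and how CT is converted, so that the direction matches (AUC_PL − AUC_LY)/AUC_PL.
4. Report sensitivity to the substituted value, for example the LLOQ and a lower value.

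The cost is a few sentences and two or three extra runs, with no new data. As the sponsor is unblinded, the choice should be fixed before any AUC is calculated. The downside is that on a log scale the estimate depends on the substituted value (6 to 16 log10-days at the LLOQ against 17 to 26 at 0 log10 in the simulation), so the sensitivity results must be reported beside it.

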9.4.1. General Considerations

Method	Analysis
Descriptive Statistics	number of participants, mean, standard deviation,
	median, minimum, and maximum for continuous
	measures, and frequency counts and percentages for
	categorical measures
Kaplan-Meier curves and summary statistics	Time-to-event analysis
Logistic regression analysis	Treatment comparisons of binary variables with
	treatment in the model.
Nonparametric	Treatment comparison of ordinal variables.
(for example, Mann-Whitney or van Elteren tests)	
Analysis of variance or analysis of covariance	Treatment comparisons of continuous variables
	following appropriate transformations, if necessary

This table describes the general statistical methods that may be used in this study.

Adjustments for other factors, if any, will be described in the SAP.

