Additional analyses on viral clearance, such as logistic regression with treatment as a fixed effect, may be conducted as deemed appropriate and where sufficient data are available.

Time to SARS-CoV-2 clearance

The time to SARS-CoV-2 clearance will be summarized by treatment, and listed.

In addition, a graphical presentation of the clearance times will be provided using a Kaplan-Meier plot.

Viral Resistance to LY3819253

Participant who show signs of viral resistance will be summarized in frequency tables by treatment and listed.

PK/PD Modeling

Additional PK/PD exposure-response modeling of viral dynamics may be conducted. These analyses will be the responsibility of Eli Lilly PK/PD group.

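### The exploratory comparison of viral clearance leaves out baseline viral load, which the SAP's other viral-load models include

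*SAP*

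**What the plan says.** For clearance (yes/no), SAP 10.4.2 says that the number of patients with "SARS-Cov-2 clearance will be analyzed using a Chi-square test to compare LY3819253 versus pooled placebo at each dose level", on the condition "if there are sufficient data available". The example code is "table trtmnt*clear / chisq all", a plain table of counts with no stratum or covariate. The next paragraph adds: "Additional analyses on viral clearance, such as logistic regression with treatment as a fixed effect, may be conducted as deemed appropriate". Time to clearance gets a summary and a Kaplan-Meier plot, with no between-arm test.

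The same section treats the other viral-load measures differently. For the MMRM on change from baseline: "The model will contain baseline as a covariate, treatment, day and treatment-by-day interaction as fixed effects". For the AUC: "The model will contain treatment as a fixed effect and baseline viral load as a covariate". The Bayesian model for change from baseline also carries a coefficient on baseline viral load, and its AUC counterpart drops only the day, interaction and within-subject error terms.

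Protocol 9.4.1 leaves the choice of covariates to the SAP: "Adjustments for other factors, if any, will be described in the SAP". The SAP names none for clearance. The Schedule of Activities places a swab before the infusion on Day 1, so the covariate needs no extra sampling.

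**The concern.** Clearance is two consecutive negative swabs. A participant who starts with less virus has less far to fall, so it is reasonable to expect baseline to predict clearance. The sponsor's other models already treat baseline as relevant. No stratification by viral load is described in Protocol 6.3.

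Two things follow if baseline is prognostic. In a comparison the size of Cohort 4, an unadjusted test discards information and loses power. In Cohorts 1-3, with 6 on each dose and 6 pooled placebo, the arms can differ noticeably in starting viral load by chance. A dose arm that happens to start lower would then look as though it clears virus better. Protocol 4.3 says Cohort 4 may be used for dose selection in later studies, so a misread clearance pattern could carry forward.

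**Working it through.** **No figure to reproduce.** The plan states no power, alpha, clearance rate or prognostic strength for this comparison.

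**Inputs from the documents**
- 6 active and 2 placebo in each of Cohorts 1-3 (SAP 6), with placebo pooled over cohorts (SAP 7).
- Optional Cohort 4 of up to 100, about 1:1 (SAP 8).
- Comparisons are therefore 6 v 6 without Cohort 4. With it, pooled placebo is 6 + 50 = 56, giving 6 v 56 for the earlier doses and 50 v 56 for a distinct Cohort 4 dose.

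**Assumptions**
- Clearance 40% on placebo and 65% on active.
- Two-sided alpha 0.10, to match the 90% CIs of the other pharmacodynamic models.
- Log-odds of clearance change by b = 0, -0.5, -1.0 or -1.5 per SD of baseline viral load.

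**Step 1: chance imbalance.** In baseline-SD units, the SD of the difference in arm means is √(1/n1 + 1/n0).
- 6 v 6: √(1/6 + 1/6) = 0.58
- 6 v 56: √(1/6 + 1/56) = 0.43
- 50 v 56: √(1/50 + 1/56) = 0.19

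**Step 2: effect on the unadjusted difference.** With no drug effect, the simulated change in proportion cleared per baseline SD was about 0.11, 0.20 and 0.26 for b = -0.5, -1.0 and -1.5. Multiplying by Step 1 gives the shift for a one-SD imbalance.

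| Comparison | b = -0.5 | b = -1.0 | b = -1.5 |
|---|---|---|---|
| 6 v 6 | 6 points | 12 points | 15 points |
| 6 v 56 | 5 points | 9 points | 11 points |
| 50 v 56 | 2 points | 4 points | 5 points |

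A second simulation gave 6 to 16 points at 6 v 6. It assumed a mean baseline of 5 log10, a detection limit of 2 log10, a decline of 0.28 log10/day (SD 0.10), assay error SD 0.6, and clearance by Day 15.

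**Step 3: power at Cohort 4 size (50 v 56).** For the chi-square:
- Pooled proportion = (56 × 0.40 + 50 × 0.65)/106 = 0.518.
- SE under the null = √(0.518 × 0.482 × (1/56 + 1/50)) = 0.0972.
- SE under the alternative = √(0.24/56 + 0.2275/50) = 0.0940.
- Power = Φ((0.25 - 1.645 × 0.0972)/0.0940) = Φ(0.96) = 83%.

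Simulated power with baseline in a logistic model was 83%, 85%, 89% and 93% for b = 0, -0.5, -1.0 and -1.5. The differences, taken before rounding, are about 0, 2, 6 and 9 points. A repeat run gave 87%, 89% and 92% adjusted against 83-84% unadjusted for the three non-zero values of b. Error was near 10% for both methods.

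**Step 4: the 6 v 6 comparison, nominal error 10%**

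| Method | Error | Power |
|---|---|---|
| Chi-square | 13-15% | 28-31% |
| Ordinary adjusted logistic | about 18% | 29-34% |
| Firth-penalised adjusted logistic | 7-10% | 18-23% |

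The ordinary adjusted fit separated in 14-28% of trials. The power column is not like for like, because the first two methods exceed their nominal error. An exact permutation test adjusted for baseline had power of 20% when b = 0 and 21-26% otherwise, so only 1 to 6 points come from baseline prognosis.

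The form of penalised inference also matters. Under the viral-decline assumptions above, with baseline SD 0.7, 1.1 and 1.8 log10 and one-sided 0.05, Firth power at 6 v 6 was 15%, 15% and 11% with the profile likelihood but 6%, 5% and 3% with Wald tests.

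**The case against.** The sponsor can fairly say four things.

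- **Validity is not at issue.** Averaged over randomization, the chi-square is not biased by a missing covariate, and its error in the larger comparisons was 10-11% at a nominal 10%. The excess at 6 v 6 comes from small counts. This stands. A reader might infer that the planned test is biased, but the shift in Step 2 is conditional on an imbalance that has occurred. A reader might also infer a systematic difference because placebo is pooled over sequential cohorts, but the documents give no evidence that baseline viral load drifts between cohorts.
- **The stakes are low.** The proportion cleared is exploratory (SAP 5.3), all tests are exploratory without multiplicity control (Protocol 9.1), and the test runs only if data suffice. The viral-load change and AUC analyses already adjust. This stands and limits the severity.
- **The optional model is only an example.** The wording "such as logistic regression with treatment as a fixed effect, may be conducted as deemed appropriate" does not forbid a covariate. That is true, but it does not prespecify one either, and the planned test cannot carry one.
- **A baseline term could drop participants.** The pharmacodynamic population (SAP 9) requires a post-baseline value but not a baseline one, and the AUC rule anticipates missing Day 1 values. The clearance derivation keeps people by setting missing swabs to positive. This stands, so the fix needs a rule for it.

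**Conclusion.** The omission is real, and its consequence is modest. At about 50 v 56 the loss is roughly 2 to 9 points of power for b between -0.5 and -1.5, and nothing if baseline is not prognostic. It arises only if Cohort 4 enrols. At 6 per arm the case for adjusting is protection against a chance imbalance worth about 6 to 16 points in the proportion cleared, together with better error control from the penalised model. All these sizes depend on assumed clearance rates and prognostic strengths.

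Three stronger readings are tempting but unsupported.
- **Power is lost in every cohort.** At 6 v 6 the penalised adjusted model shows no gain.
- **The loss could reach 15 points.** The viral-decline simulation did give 56% v 72% at 50 v 50, but only with an assumed baseline SD of 1.8 log10 and a correlation of 0.72 between baseline and clearance time. Nothing in the documents supports values that high.
- **Clearance is the viral endpoint most sensitive to starting level.** The documents do not show this, and the AUC contains the baseline value itself.

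Time to clearance has no planned between-arm test, so this point does not extend to it.

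**What to change.** In SAP 10.4.2:
- Make the between-arm clearance comparison a logistic regression on treatment plus baseline viral load at Days 7, 11, 15 and 22.
- Where cells are sparse, use a Firth penalised likelihood with profile-likelihood inference, not Wald.
- Report baseline-standardised differences in proportion cleared with 90% CIs, in line with the other pharmacodynamic models.
- State a simple rule that keeps participants with a missing Day 1 viral load in the model, for example single mean imputation of the baseline covariate.
- Keep the raw frequency table, the chi-square as a supportive analysis, and the Kaplan-Meier plot as a descriptive display.

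The cost is SAP wording and a few lines of code, with no new sampling. The downside is one more model term and a somewhat conservative penalised fit at 6 per arm.
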